**Day 0:**

1. Assessment of clinical status by standard symptom and physical examination including calculation of SOFA score in ICU patients. SOFA score will be calculated as per Appendix 1.
2. Study Plasma Administration: 1-2 units of plasma will be transfused. Time at start and end time of infusion will be recorded and vital signs will be measured immediately prior to infusion, 10-20 minutes after start of infusion, at completion of infusion and 30-60 minutes after the end of the infusion.
3. New medical conditions, concomitant medication, and AE evaluation
4. Physical examination
5. CBC with Diff, comprehensive metabolic panel, DIC panel, ferritin, LDH, immunoglobulin panel, and C-reactive protein
6. Research Samples as detailed in Table 1 (Schedule of events)

**Days 1-14 (or for duration of hospitalization) – Refer to table 1 for specific day:**

1. Vital signs daily
2. COVID-19 symptom screen (fevers, cough, shortness of breath)
3. Assessment of clinical status
4. New medical conditions, concomitant medication, and AE evaluation
5. Physical examination
6. SOFA score
7. CBC with Diff, comprehensive metabolic panel, CRP, Ferritin, DIC panel, LDH
8. Research Samples as detailed in Table 1 (Schedule of events)

**Day 28 (Refer to Table 1):**

Follow-up by phone is acceptable if alive and at home.

Current admission; at home vs. in hospital (ICU or not), on supplemental O2 or not, back to work (fully, partially, SNF, nursing home, LTAC)

1. COVID-19 symptom screen (fevers, cough, shortness of breath)
2. SOFA score if in ICU
3. Assessment of clinical status with physical exam if in hospital / clinic
4. New medical conditions, concomitant medication, and AE evaluation
5. If still hospitalized, follow procedures listed in table 1.
6. Optional labs (CBC with Diff, comprehensive metabolic panel, CRP, Ferritin, DIC panel, LDH; Research Labs) – all labs beyond day 14 are optional.

**9. Efficacy, virology measures:**

**Clinical Efficacy**

Clinical assessment will be standard of care subjective symptom assessment and physical examination as documented in daily progress notes. SOFA score will be documented for ICU resident patients.

## **Virologic measures**

1. Serologic positivity and neutralization antibody titers for anti-SARS-CoV-2 at days 0, 4, 7 and 14, whenever possible given sample availability, patient mortality, reluctance to come to MCW for testing.

## **10. Risks and benefits**

Potential Benefits of treatment:

The potential benefits of antiviral treatment with anti-SARS CoV-2 plasma in patients with respiratory symptoms consistent with interstitial pneumonia at high risk for requiring ICU admission are not known. However, it is anticipated that treatment will decrease the risk of disease progression requiring ICU admission and aggressive respiratory support including possible mechanical ventilation (and other ICU support).

Potential benefits of clinical monitoring and virologic testing:

Subjects enrolled in the study may reduce their chances of disease progression.

Potential risks:

1. Risks of plasma: Fever, chills, rash, headache, serious allergic reactions, TRALI, TACO, transmission of infectious agents
2. Risks of phlebotomy: local discomfort, bruising, hematoma, bleeding, fainting
3. Total blood draws will not exceed 100 mL during the entire study
4. Risks of oropharyngeal and throat swab: local discomfort, vomiting

Alternatives:

The alternative to participation in this study is routine care and or other clinical trials.

Participation in this trial does not preclude enrollment in any other clinical trial.

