### **Laboratory Objectives:**

1. Anti-SARS-CoV-2 antibody titers at days 0, 4, 7 and 14 (additional days 21 and 28 may be included, as available).
2. SARS-CoV-2 RNA by RT-PCR at days 7 and 14.
3. Research blood draws on days 0, 4, 7, 14, and 28 to investigate immunology and hematologic pathways in severe COVID-19.

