## 5.2 Table 1: Schedule of Events

Study period	Screen	Baseline Prior to plasma	Transfusion	Follow-up 					Monthly follow-up 
Day	-3 to 0	0	0	1	4	7	14	28	60
Eligibility									
Informed consent	x								
Demographic and medical history	x								
COVID-19 symptom screen	x								
Chest x-ray or chest CT	x								
SARS-CoV-2 RT-PCR for eligibility	x								
Serum/urine pregnancy test in FCBP w/in 7 days of study transfusion	x								
ABO type and antibody screen	x								
Treatment									
Donor Plasma Administration			x						
Drug infusion			x						
Study Procedures									
Vital signs	x	x	x 	Daily clinical assessments during hospital stay. SOFA score in ICU patients					
Physical examination	x	x							
Symptom screen	x	x							x
Concomitant medications	x	x		x	x	x	x	x	x
SOFA score 		x		x	x	x	x		
Adverse event monitoring	x	x	x	Throughout study period					
Laboratory testing									
CBC diff / CMP/ DIC panel		x		x	x	x	x		x 
Ferritin/CRP/LDH		x		x	x	x	x		x 
Immunoglobulin Panel		x							
SARS-CoV-2 RT-PCR		x 							
SARS-CoV-2 antibody research blood sample 		x		x	x	x	x	x 	
Research Blood Samples to Versiti 		x		x	x	x	x	x 	

1. All labs after the day of discharge from hospital are optional.
2. Refer to appendix 1.
3. Vital signs will be measured immediately prior to infusion, 10-20 minutes after start of infusion, at completion of infusion and 30-60 minutes after the end of the infusion.
4. Refer to section 14 and appendix 2.
5. Baseline RT PCR for study entry is adequate.
6. +/- 2-day window

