### **14. Research Sample Disposition:**

Research samples will be drawn from enrolled patients throughout the course of their hospitalization to investigate the early immune response and the impact of treatment. In coordination with these studies, the development of the adaptive, or immune memory response will be investigated. These samples will be drawn in coordination with clinical labs and the blood volume will be limited to 30 ml. These blood samples will be processed and studied at the Versiti Blood Research Institute in the labs of Drs. [name], [name], [name], [name], [name], [name], and [name]. [name] as lab investigator will be in overall control of sample security and distribution to other investigators named above. Immunologic and hemostatic assays will be performed on these samples in compliance with Medical College of Wisconsin safety guidelines. Research assays will include in vitro studies of lymphocyte and antibody development, mediators of the immune response particularly circulating cytokines, hemostasis, and platelet function.

Blood samples will be obtained per Table 1 and appendix 2. This will consist of 20ml citrate (blue-topped) and 10ml EDTA (purple-topped) tubes. If the collected blood volume is limited by clinical condition, sample collection will be limited to 10ml citrate and 10ml EDTA initially, then a 10ml citrate tube. Blood samples will be de-identified with only study ID# (refer to section 8), and date/time of collection. These samples will be processed at Versiti Blood Research Institute to obtain platelet-poor plasma (PPP), platelet-rich plasma (PRP), and enriched platelet and peripheral blood mononuclear cell (PBMC) samples. Samples will then be analyzed. Residual de-identified sample will be stored for batched analyses at -70C or in liquid nitrogen.

Proposed research activities will take place in the laboratories at the Versiti Blood Research Institute. Once collected, samples will be shipped deidentified to the Versiti BRI and received by [name] or designee and processed further for research tests as indicated above. Collection, storage, and communication of research samples will be conducted in a manner that is compliant with HIPAA regulations.

Refer to appendix 2 for further collection and shipping instructions.

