## APPENDIX 2: Research Blood Sample Collection and Shipping Instructions

### Specimen Collection & Handling

#### Peripheral blood collection:

Blood samples will be obtained per Table 1 time points.

Approximately 30ml of whole blood will be collected: 20ml in citrate (blue-topped) and 10ml in EDTA (purple-topped) tubes.

If the collected blood volume is limited by clinical condition, sample collection will be limited to 10ml in citrate and 10ml in an EDTA tube initially, then 10ml in a citrate tube.

No pre-processing is required.

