**Peripheral Blood Research Sample Information:**

Date of Sample Collection: \_\_\_\_\_ Time of Sample Collection: \_\_\_\_\_

Time point of collection:

- Baseline
- Day 4
- Day 7
- Day 14
- Day 28

Person Completing Requisition and Transporting Sample: \_\_\_\_\_

Phone Number and Email of Person Completing Requisition: \_\_\_\_\_

Date and Time of Transport of Sample: \_\_\_\_\_

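### The 100 mL limit on total blood draws cannot be met by a patient sampled at the standard 30 mL through Day 14: the research tubes alone come to 120 or 150 mL

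*Combined protocol and SAP*

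**What the plan says.** Section 10 (Risks and benefits) lists this among the potential risks: "Total blood draws will not exceed 100 mL during the entire study". It does not say whether the limit covers research tubes only or all blood that the protocol schedules.

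The volume per collection is in Appendix 2: "Approximately 30ml of whole blood will be collected: 20ml in citrate (blue-topped) and 10ml in EDTA (purple-topped) tubes", with timing given as "Blood samples will be obtained per Table 1 time points". Section 14 names the same tubes and says that "the blood volume will be limited to 30 ml", without stating whether that is per draw or in total. Both places allow a smaller collection when the patient's condition restricts how much can be drawn: 10 mL citrate plus 10 mL EDTA first, and a 10 mL citrate tube after that.

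The draw days differ between sections:

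- The laboratory objectives (Protocol Summary and Section 4.1) give five: "Research blood draws on days 0, 4, 7, 14, and 28".
- Table 1 (Section 5.2), in the row "Research Blood Samples to Versiti", marks six: baseline and Days 1, 4, 7, 14 and 28.
- The requisition form in Appendix 2, under "Time point of collection", offers five boxes: baseline and Days 4, 7, 14 and 28. It has none for Day 1.

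Table 1 footnote 1 makes laboratory tests after discharge optional. The Day 28 entry in Section 8 makes all those after Day 14 optional.

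**The concern.** The limit is the protocol's only figure for the total amount of blood taken from a participant. Multiplying the protocol's own volume by its own draw days gives more than that figure, so staff cannot follow both the standard schedule and the limit for a patient who stays in hospital through Day 14. At stake are the accuracy of a stated burden on seriously ill patients and a sampling schedule that sites can carry out as written. The unmatched Day 1 draw adds to this, because the number of collections depends on which section is read.

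**Working it through.** **Inputs**

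- Limit: 100 mL per participant (Section 10).
- Standard volume: v = 20 + 10 = 30 mL per collection (Appendix 2; same tubes in Section 14).
- Number of collections, n:
  - objectives' days through Day 14: n = 4
  - objectives' days or requisition form with Day 28: n = 5
  - Table 1 through Day 14: n = 5
  - Table 1 with Day 28: n = 6

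**The plan's own figure.** The protocol gives no derivation of 100 mL, and no listed schedule at the standard volume reproduces it. Since 100 / 30 = 3.3, at most three full collections (90 mL) fit.

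**Standard volume, total = n x 30**

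| Schedule | n | Total (mL) | Over limit (mL) |
|---|---|---|---|
| Objectives, through Day 14 | 4 | 120 | 20 |
| Objectives, with optional Day 28 | 5 | 150 | 50 |
| Table 1, through Day 14 | 5 | 150 | 50 |
| Table 1, with optional Day 28 | 6 | 180 | 80 |

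Against a limit of 100 mL, the excess in mL is also the excess in percent.

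**Early discharge, no optional draws.** With draws on Days 0 and 4 the total is 2 x 30 = 60 mL. With Days 0, 1 and 4, or Days 0, 4 and 7, it is 3 x 30 = 90 mL. All are within the limit.

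**Reduced-volume exception.** The wording can be read in more than one way.

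- 20 mL at every collection: n x 20 = 80, 100 and 120 mL for n = 4, 5 and 6. Six collections still exceed the limit.
- 20 mL at the first collection and 10 mL at each later one: 20 + 10(n - 1) = 50, 60 and 70 mL. All are within the limit.
- It may instead describe the order in which tubes are filled within one collection, in which case it does not fix a total.

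**Is 30 mL per collection or a study total?** Spread over five or six collections, a 30 mL study total would be 30/5 = 6 mL or 30/6 = 5 mL each. Neither matches the 10 and 20 mL amounts named. Appendix 2 ties the collection to the Table 1 time points, and the requisition form is completed for each collection with a time-point box. The per-collection reading is therefore the natural one.

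**Not counted.** Table 1 also schedules clinical panels (CBC, metabolic and DIC panels, ferritin, CRP, LDH) and has a separate row for an antibody research sample. The documents give no volumes for these. If the limit covers them and they need their own tubes, the totals above are lower bounds.

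**The case against.** The strongest reply is that the limit may hold for many patients. Day 28 and all post-discharge samples are optional, so 180 mL is not a routine total: it needs the optional Day 28 draw and the Day 1 draw that only Table 1 schedules. A patient who leaves hospital before Day 14, with full draws on Days 0, 4 and 7, gives 90 mL. The reduced-volume exception can also bring the total down to 50-100 mL on most readings. And Section 14, read alone, could mean 30 mL for the whole study.

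The first two points stand as limits on who is affected. They do not rescue the limit for a patient in hospital through Day 14 and sampled at the standard volume, because even the shortest listed schedule gives 120 mL. The exception depends on the patient's condition and is not the standard procedure. The Section 14 reading is at odds with Appendix 2 and the requisition form; if it was intended, those need correcting instead.

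A reader might also infer that sites obeying the limit would stop after three full draws and so lose Day 7 or Day 14 antibody titers selectively in the patients who stay longest. The documents do not support that:

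- After three full draws 100 - 90 = 10 mL remains, enough for one 10 mL tube, and no assay volume is given to show that titers need the full 30 mL.
- On the objectives' days, Day 7 is the third draw and is kept.
- Later samples are already optional for patients discharged early, so the direction of any imbalance is not established.
- Section 9 collects titers only as availability allows, and Section 7.2 analyses them mainly descriptively.

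**Conclusion.** The point holds for patients sampled at the standard volume through Day 14. Research tubes alone take 120 mL on the objectives' days or 150 mL on Table 1's days, which is 20 or 50 mL over the stated maximum. With the optional Day 28 sample the totals are 150 or 180 mL. This assumes that 30 mL is per collection and that the reduced-volume exception is not used. The limit is not broken for every participant: three or fewer full draws stay at or below 90 mL. Separately, and whatever the volume, Table 1 schedules a Day 1 research draw that the objectives and the requisition form lack.

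This is an inconsistency in a stated participant burden. It should be corrected, but it touches no primary endpoint, hypothesis test or sample size.

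**What to change.** 1. Use one list of research draw days in the laboratory objectives (Protocol Summary and Section 4.1), Table 1 and the requisition form, and decide whether Day 1 belongs on it.
2. State in Section 14 and Appendix 2 that 30 mL is per draw, and say which reading of the reduced-volume exception is meant.
3. State in Section 10 whether the limit covers research tubes only or also the clinical laboratory tubes that the protocol schedules. This must come before any new total is written.
4. Make the total and the schedule agree, in one of two ways:
   - Restate the maximum. For research tubes this is 5 x 30 = 150 mL for five draws or 6 x 30 = 180 mL for six, plus the clinical tubes if they count.
   - Reduce the research volume so that draws x volume is at most 100 mL: 100/5 = 20 mL for five draws or 100/6 = about 16.7 mL for six, and less if clinical tubes count.
5. Check whether the consent form carries the 100 mL figure, and align it if so. The consent pages are not in the reviewed text.

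The cost is a change of wording, with either a less favourable stated burden or less blood for the ancillary assays.

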## **11. Safety measures**

1. Laboratory evaluations consistent with ongoing standard medical care may include radiographic imaging modalities such as chest x-rays and chest CT.
2. Clinical assessment and monitoring for infusion reaction on day of infusion as per standard of care blood transfusion guidelines.
3. Safety laboratory tests (ABO typing, pregnancy testing, CBC, CRP, and comprehensive metabolic panel) will be performed at the local CLIA-certified clinical laboratory as per schedule of assessments in Table 1.

### **11.1 Adverse Event**

Any untoward medical occurrence in a clinical investigation subject who has received a study intervention and that does not necessarily have to have a causal relationship with the study product. An AE can, therefore, be any unfavorable and unintended sign (including an abnormal laboratory finding, for example), symptom, or disease temporally associated with the use of the study product, whether or not considered related to the study product.

Unexpected Adverse event: (UAE) An adverse reaction attributed to infused plasma, the nature or severity of which is not consistent with the risks outlined in the consent form.

This study will utilize the NCI Common Terminology Criteria for Adverse Events (CTCAE) version 5.0, located on the CTEP web site:

[http://ctep.cancer.gov/protocolDevelopment/electronic\\_applications/ctc.htm](http://ctep.cancer.gov/protocolDevelopment/electronic_applications/ctc.htm)

## **11.2 Serious Adverse Event (SAE)**

An SAE is any adverse event that results in any of the following outcomes:

1. Death
2. Life-threatening (immediate risk of death)
3. Prolongation of existing hospitalization
4. Persistent or significant disability or incapacity
5. Important medical events that may not result in death, be life threatening, or require intervention or escalation of care may be considered a serious adverse event when, based upon appropriate medical judgment, they may jeopardize the subject and may require medical or surgical intervention to prevent one of the outcomes listed in this definition. Examples of such medical events include allergic bronchospasm requiring intensive treatment in an emergency room or at home, blood dyscrasias or convulsions that do not result in inpatient hospitalization.

### **11.2.1 SAEs are reported in the following manner:**

All fatal or life-threatening or unexpected and suspected SAEs will be reported to the IRB and all applicable agencies within 24 hours and all other SAEs (non-fatal or non-life-threatening) within 4 calendar days of study site staff awareness.

- Every SAE regardless of suspected causality (e.g., relationship to study drugs or study procedure) occurring after the subject has signed the consent through the 30 days after the last dose of study drugs, AND only SAEs occurring more than 30 days after the last dose of study drugs that the investigator suspects a causal relationship to study plasma, must be reported in the study database SAE section. These will also be reported to the ISM ([name] as below) and the IRB. All transfusion related AEs and SAEs have to be reported to the hospital blood bank additionally in order to start a transfusion AE investigation.
- All grade 4 and 5 SAEs and any other expedited SAE report to IRB must also be reported to FDA (MedWatch 3500A described below) within five calendar days of MCW study staff's awareness.

- In addition: if the SAE is unexpected and has a suspected relationship to the study drug, site must create a reportable event notice with the MCW IRB, ISM and complete a MedWatch 3500A and submit to FDA:
  - US FDA MedWatch 3500A found here:  
<http://www.fda.gov/Safety/MedWatch/HowToReport/DownloadForms/default.htm>

### **11.2.2 Unanticipated Problem Involving Risk to Subject or Other (UPIRSO)**

The Office for Human Research Protections (OHRP) considers unanticipated problems involving risks to participants or others to include, in general, any incident, experience, or outcome that meets all of the following criteria:

- Unexpected in terms of nature, severity, or frequency given (a) the research procedures that are described in the protocol-related documents, such as the Institutional Review Board (sIRB)-approved research protocol and informed consent document; and (b) the characteristics of the participant population being studied.
- Related or possibly related to participation in the research (“possibly related” means there is a reasonable possibility that the incident, experience, or outcome may have been caused by the procedures involved in the research).
- Suggests that the research places participants or others at a greater risk of harm (including physical, psychological, economic, or social harm) than was previously known or recognized.

### **11.2.3 Adverse Events Not Meeting SAE Definition**

- Any medical condition that is present at the time that the participant is screened will be considered as baseline condition and captured on the baseline CRF form, not reported as an AE. All new or worsening AEs that occur after starting study drug until 30 days post last dose of study plasma will be tracked and followed until resolution, stabilization of the event as chronic, subject withdraws consent, or is lost to follow-up (including subjects who discontinue early).
- Changes in the grade of an AE will be documented in the AE CRF to allow an assessment of the duration of the event at each level of severity to be performed. Information to be collected includes event description, time of onset, clinician’s assessment of severity, expectedness, relationship to study product (assessed only by those with the training and authority to make a diagnosis), and time of resolution/stabilization of the event.

### **11.2.4 Protocol Deviation**

A deviation from the IRB-approved study procedures designated as serious:

1. Serious Protocol Deviation: protocol deviation that is also an SAE and/or compromises the safety, welfare or rights of subjects or others
2. Follow safety reporting requirements listed above

### **11.3 Reporting Interval**

All AEs and SAEs will be documented from consenting until study completion at 60 days from study infusion or death or discontinuation from the study. All AEs and SAEs will be followed until resolution even if this extends beyond the study-reporting period. Resolution of an adverse event is defined as the

return to pre-treatment status or stabilization of the condition with the expectation that it will remain chronic.

### Investigator's Assessment of Adverse Events

The determination of seriousness, severity, and causality will be made by an on-site investigator who is qualified (licensed) to diagnose adverse event information, provide a medical evaluation of adverse events, and classify adverse events based upon medical judgment. This includes but is not limited to physicians, physician assistants, and nurse practitioners.

#### Assessment of Seriousness

1. Event seriousness will be determined according to the protocol definition of an SAE
2. Assessment of Severity

Event severity will be assigned according to the scale below

1 = Mild: Transient or mild discomfort (<48 hours); no medical intervention/therapy required.)

2 = Moderate: Some worsening of symptoms but no or minimal medical intervention/therapy required)

3 = Severe: Escalation of medical intervention/therapy required

4 = Life-threatening: Marked escalation of medical intervention/therapy required.

5= Death

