### 7.1 Analysis of AE data

Analysis of AE data will primarily be descriptive based on MedDRA coding of events. The proportion of subjects experiencing an SAE and the proportion experiencing a Grade 3 or higher event will be presented.

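### Two unreconciled severity scales leave the Grade 3+ laboratory halt and the Grade 3+ proportion ambiguous; the SAE list omits new hospitalization, and AE windows of 30 and 60 days conflict

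*Combined protocol and SAP*

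**What the plan says.** **Severity.** Section 11.1 states: "This study will utilize the NCI Common Terminology Criteria for Adverse Events (CTCAE) version 5.0". It does not say whether this covers event terms, grading or both. The same section counts as an adverse event "any unfavorable and unintended sign (including an abnormal laboratory finding, for example". Under Assessment of Seriousness, following section 11.3, the protocol then says "Event severity will be assigned according to the scale below" and lists five levels. The second is "2 = Moderate: Some worsening of symptoms but no or minimal medical intervention/therapy required" and the third is "3 = Severe: Escalation of medical intervention/therapy required". The fourth needs marked escalation and the fifth is death. No level has a laboratory threshold, and laboratory events are not exempted.

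**Where the grade is used.** Section 7.1: "The proportion of subjects experiencing an SAE and the proportion experiencing a Grade 3 or higher event will be presented". Section 12.2 item 4 stops enrollment and dosing when two subjects have a product-associated laboratory toxicity of Grade 3 or above on the same parameter. Neither place names a scale.

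**Seriousness.** "Event seriousness will be determined according to the protocol definition of an SAE". The list in section 11.2 has death, immediate risk of death, a lengthened current stay, disability, and important medical events by judgment. New inpatient admission is not on it.

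**Windows.** Section 11.3 documents all AEs and SAEs from consent to day 60. Section 11.2.1 puts SAEs of any cause in the study database only to 30 days after plasma, and later ones only if a causal link is suspected. Section 11.2.3 tracks non-serious AEs from the start of study drug to day 30. Section 8 records new conditions from consent onward, yet section 11.1 defines an AE as "Any untoward medical occurrence in a clinical investigation subject who has received a study intervention".

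**The concern.** The trial is single-arm, so the safety proportions in 7.1 stand alone. No control group, graded the same way, would absorb a difference in grading or in collection period. If two careful graders can assign different grades to one event, or two data managers can close collection on different days, the reported proportions cannot be reproduced from the protocol.

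The halting rule is the sharper issue. Item 3 of section 12.2 already stops the study for a single product-associated SAE. What item 4 adds is therefore non-serious laboratory toxicity, some of which will be handled without escalating therapy. That is exactly where the protocol's own scale cannot give a Grade 3.

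**Working it through.** The plan states no figure to reproduce here. The check sets the rules side by side, with simple day counts for the windows.

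**1. Severity scale**

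Take a laboratory abnormality that is not fatal and leads to no escalation of treatment.

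- It is an AE under section 11.1.
- On the scale following 11.3, Grade 3 needs escalation, Grade 4 needs marked escalation and Grade 5 is death. The event is therefore Grade 2 at most, whatever the value.
- On CTCAE v5.0 the grade may differ. The cut-offs are not in the documents, so I assume only that CTCAE can grade laboratory values.

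On the protocol's scale the event counts neither toward item 4 nor toward the Grade 3+ proportion. On CTCAE it may count toward both. For item 4 it must also be product-associated. The Assessment of Association text requires a temporal relation and no other explanation.

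The documents contain no event data, so neither the size nor the direction of the shift in the 7.1 proportion can be computed.

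**2. SAE list**

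- All subjects are inpatients at entry (section 5.1), so the gap opens only after discharge.
- Section 4.2 follows subjects to day 60, and section 8 allows the day 28 contact by phone for those at home.
- A readmission that is not fatal, life-threatening or disabling meets no listed criterion automatically. It counts only if judged an important medical event under item 5.
- The examples in item 5 include events that did not lead to admission. That wording makes sense only if admission is itself a criterion, which suggests the line was left out.

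**3. Windows**

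Inputs: screening from day -3 to 0 (Table 1); one infusion on day 0, so the last dose is day 0; cut-offs at day 30 (11.2.1, 11.2.3) and day 60 (11.3). The plus or minus 2-day visit windows are ignored.

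| Event type | Narrower rule | Section 11.3 | Days in dispute |
|---|---|---|---|
| Non-serious AE | day 0 to 30 (11.2.3) | up to day -3, to day 60 | up to 3 + (60 - 30) = 33 |
| SAE judged unrelated | consent to day 30 (11.2.1) | consent to day 60 | 60 - 30 = 30 |
| SAE suspected related to plasma | no end at day 30 (11.2.1) | consent to day 60 | 0 |

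The longest window is 3 + 60 = 63 days. After day 30, Table 1 has one scheduled contact, at day 60. Section 11.1 gives a definition and no window, so it adds no days to the SAE count. Its wording nevertheless does not fit a start at consent.

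**The case against.** **One scale already governs.** Only the text following 11.3 says how severity is to be assigned. Section 11.1 merely says CTCAE will be used, and 11.2.3 treats grade and severity level as the same thing. A specific instruction can override a general one. For clinical events this is a fair reading, though an unstated one. CTCAE as a source of terms alone is less natural, because 7.1 already names MedDRA for coding. For laboratory events the reading makes matters worse, since item 4 then rests on a scale without laboratory criteria. Taking the laboratory toxicity of item 4 to mean CTCAE is sensible, but site staff would have to infer it.

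**The halt has backstops.** This stands. Item 3 stops for one product-associated SAE, item 5 covers a worrying laboratory pattern, and the study physician or the independent safety monitor can stop on judgment. The association requirement removes many laboratory abnormalities in this population on either scale. A reader might infer that the trial could not be stopped for laboratory toxicity. The documents do not support that: only the automatic trigger is affected.

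**Readmissions and reporting.** Seriousness is assessed with medical judgment, so many readmissions would still be called serious. That narrows the second part without removing it. Nor can one separate documenting from reporting to reconcile the windows, because 11.2.1 concerns entry in the study database.

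**Wider inferences.** A reader might use the number of scheduled laboratory draws as the size of the problem. That counts visits and says nothing about how many events would change grade. A reader might also fear that FDA reporting of fatal or life-threatening SAEs depends on the scale. Under 11.2.1 these go to the IRB within 24 hours and, as expedited reports, to the FDA, whatever the grade.

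**Conclusion.** The text is wrong as written, and the consequence is minor to moderate. The scale conflict carries most of the weight. It leaves the Grade 3+ proportion in 7.1 dependent on an unstated choice. Under the protocol's own scale, item 4 would miss product-associated, non-serious laboratory toxicities that prompt no escalation. The missing hospitalization criterion can understate the SAE proportion in 7.1. The window conflict affects recording and the descriptive summaries: up to 33 days for non-serious AEs, 30 for unrelated SAEs and none for plasma-suspected SAEs.

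This rests on two assumptions: that consent can fall as early as day -3, and that CTCAE v5.0 can grade laboratory values. The number of subjects reclassified cannot be derived from the documents. The efficacy tests, the 12-hour respiratory deterioration endpoint and the capture window for plasma-attributed SAEs are unaffected.

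**What to change.** 1. **Scale.** Grade by CTCAE v5.0, at minimum for all laboratory events. Keep the protocol's own scale only for terms that CTCAE does not grade. Name this rule in 7.1 and in 12.2 item 4. Writing laboratory criteria into the protocol's scale would also work; what matters is that one rule is stated.
2. **SAE list.** Add inpatient hospitalization, including readmission after discharge, to section 11.2.
3. **Windows.** Record all AEs and SAEs in the database from consent to day 60, as 11.3 already requires, and bring 11.2.1 and 11.2.3 into line. Reword the 11.1 definition to fit a start at consent. In 7.1, summarise events with onset after infusion and list pre-infusion events separately. IRB and safety-monitor reporting of unrelated SAEs may stay at day 30.

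**Cost.** Protocol wording and CRF instructions. Some readmissions will need extra SAE reports. If IRB and safety-monitor reporting is also extended to day 60, those reports will increase too. Recording to day 60 is no new burden, since 11.3 requires it now.
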